### **Healthy subjects**

**Healthy subjects will participate only in one visit** (around 4 hours) during which they will:

- Revision of the screening forms which includes eligibility criteria and MRI screening form by the PI or study coordinator. The PI will update the physician at regular meetings about the inclusion of these subjects. If there is any doubt about inclusion criteria, the PI will ask physician for advice. However, there is no need for the signature of the physician or the nurse practitioner on the eligibility criteria given that we are including healthy subjects and we are administering only placebo spray. The nurse practitioner or the study physician will not conduct a health assessment.
- Read and sign the informed consent (no assessment of capacity is necessary).
- Complete some questionnaires: Symptom Checklist SCL-90, the interpersonal Reactivity Index, emotion rating of faces
- Complete a computer test of social learning test
- Complete a training on the face perception task and social games (as described above) and will perform quizzes
- Subjects will refrain from use of caffeinated drinks or tobacco for at least 12 hours the testing.
- Blood draw as described above 5 minutes after the spray
- Vital signs collection directly after the blood draw (no need to wait for an exact 15 minutes)
- Spray intake as described above. Subjects will think that they might be taking oxytocin or placebo. The experimenter is aware that the subject is receiving placebo. The nurses who are administering the drug are not necessarily aware of the content of the drug.
- Second blood draw 5 minutes after spray intake
- Vital signs collected
- MRI scan: Subjects will also complete the resting state, the FPT task and the ball-game inside the MRI scanner. Ideally, subjects will also start around 40 minutes after the spray intake. The timing will be more flexible given that subjects are not receiving drug.
- Participants will complete face rating questionnaire, the SLT and the EMT as well as the Toronto Alexithymia and mood questionnaire.

We will not collect physiological data on healthy subjects as we are not conducting an interview. We might be able to collect some data while they are inside the MRI scanner.

	Screening and consent, questionnaires, practice on behavioral tasks, computer tasks	Vital signs 1	Blood samples Pre	Spray (PI)	Blood samples post	Vital signs 2	MRI scan	Post MRI scan
Visit 1	X	X	X	X	X	X	Rest+ 3 tasks	Quest+ 2 tasks

**The new group of healthy subjects that we are recruiting from general population to match patients with autism will have to do two visits.**

**The first visit will consist of revision of informed consent and screening tests (that includes an IQ test and a color blindness test).**

**The second visit will be the same as above.**

### **Risks/discomforts and potential benefits**

**DNA:** A breach in confidentiality, resulting from inadvertent disclosure of genetic information to parties outside the research group, has the potential to negatively affect participant's insurability, employability or reproduction plans, and could have a negative impact on family relationships and/or could result in paternity suits or stigmatization.

**DNA methylation:** DNA methylation data is not informative for individual identification.

**Intranasal OT administration (Syntocinon):** In rare cases, nausea, vomiting, headache, irregularities of the pulse, skin rashes and allergic reactions in combination with shortage of breath, blood pressure decreases or circulatory collapse are reported as adverse effects of regular and repeated administration of Syntocinon. However, it is important to note that no serious adverse side effects have been reported following the administration of one single dose in any of the previously published studies using intranasal oxytocin.

Today, there are several studies with single doses and chronic oxytocin administration to individuals with ASD. Aoki et al. 2014 administered 24IU to 40 ASD with an average age of 29.6 and reported no adverse side effects. Auyeung et al. 2015 administered 24IU to individuals with ASD (34 years old on average) and found no serious side effects. They reported runny nose (in 3 cases with oxytocin vs 5 cases with placebo), tiredness (2 cases of oxytocin vs 3 cases with placebo), sore throat (1 case with oxytocin vs 0 case with placebo), shakiness (0 with oxytocin vs 1 case with placebo). Healthy subjects who received placebo spray reported runny nose, tiredness and mild nausea. Guastella et al. 2010 showed no difference in the number of reported side effects between oxytocin and placebo conditions in ASD (18IU or 24IU). Under oxytocin, they felt tired, relaxed and sweating. Under placebo, they felt tired, relaxed, headaches and coughing.

In a chronic administration (2months administration of 8IU, 6IU and 24IU) to ASD subjects between the ages of 10 and 14, Tachibana et al. 2013 conducted a safety study. They monitored blood pressure, urine osmolality, urine sodium concentration and serum osmolarity, serum sodium concentration and plasma OXT concentration, serum bone specific alkaline phosphatase and short memory and found no side effects. Hence, studies in the literature show that oxytocin administration is safe, especially in our study context. We do not expect serious adverse events related to oxytocin and do not expect significant differences in adverse effects between oxytocin doses and placebo.

**Blood draws:** The needle stick for the blood draw may cause momentary pain or discomfort. In rare cases, bruising at the site of the draw may occur. In rare cases, the subject may feel light-headed or faint as a result of the blood draw.

**MRI:** Potential risk to subjects without contraindications includes mild anxiety, claustrophobic reaction, and movement of ferromagnetic objects. Certain MRI scanning procedures can produce loud (>100 dB) noises, so ear protection will be provided by the use of sound-reduction earplugs. Beyond these risks, there are no known side effects of MRI to subjects without contraindications.

Participants might feel fatigued from the several hours of testing.

**Procedures for minimizing risks:**

**Genetic testing:** We recognize the sensitive nature of genetic information and the need to maintain strict confidentiality procedures for data that may ultimately be available to the wider scientific community. To minimize the risk of inadvertent disclosure of research information to outside parties, all information obtained from participants will be kept strictly confidential. No individual genetic results will be given to participants or their relatives. DNA used in this study will be assigned a code and the link to further identifying information concerning the individual will be available only to the PI. Release of data from NIMH to the wider scientific community will be in accordance with confidentiality procedures that have been established by the NIMH Genetics Initiative. We will adhere to the guiding principle that study identifiers cannot be connected with personal identifiers at any state of the data collection. Personal identifiers (i.e. name, address, email contact details) will be maintained on a secure server that follows HIPAA regulations. We will be transferring blood cells, plasma samples to other laboratory within Emory and outside Emory (after getting a permission of a medical transfer agreement). We will make sure to send de-identified coded samples. The same applies for saliva samples.

We would like to add more specific details about the processing of plasma samples. We are transferring some of the plasma samples of healthy subjects and patients with ASD from the CRN unit to [name] who is at Emory University. He will be analyzing the levels of oxytocin in plasma. The plasma samples are coded and do not contain names. However, there are some identifiers that are present on the samples: such as date of submission and other. We added [name] to the staff personnel.

We are likely to give him saliva samples too to measure DNA methylation of the oxytocin receptor gene.

**Intranasal OT administration:** With a single dose of Syntocinon, no adverse side effects of the substance are to be expected. To further minimize risk, subjects will receive OXT at Emory Hospital (CRN unit at ACTSI). To monitor potential side effects of OXT administration, temperature, heart rate and blood pressure will be measured before hormone administration and 15 minutes after hormone administration. Experimenter will again ask if the subject is experiencing any of the following symptoms: chest pain, difficulty breathing, itching. If the subject

reports any of these symptoms, the study physician or study nurse practitioner will be contacted and asked to advise on how to treat the subject and whether it is safe to continue with the protocol. If necessary, a code will be called. If no side effects are reported, but temperature has increased or decreased more than 2 degrees, heart rate is above 100 bpm, or blood pressure is above 140/90, the subject will be asked to sit quietly for 10 minutes after which vital signs will be re-measured. If vital signs are within the normal range, and no side effects are reported, they will proceed through the experiment. If not, the study physician or study nurse practitioner will be contacted and asked to advise on how to treat the subject and whether it is safe to continue with the protocol. If subjects were to experience a serious adverse event, such as a heart attack or an anaphylactic reaction, a code med will be called and, if necessary, the subject will be taken to the Emory ER. [name] or [name] and the CRN nurses will be notified by the project coordinator. [name] or [name] will call to admit the subject to the ER.

**Blood Draw:** Subjects will be monitored for signs that they may faint such as clammy skin, dizziness, confusion, irregular breathing, and decreased blood pressure. If these signs are observed, subjects will be asked to lie down with their legs elevated and blood pressure will be monitored until symptoms subside. If a subject loses consciousness and requires medical attention while in the Anthropology Building, Emory First Responders will be contacted (911). If a subject loses consciousness and requires medical attention while at the Biomedical Imaging Technology Center in Emory University Hospital, study staff will instruct the MRI technician to call a hospital code for medical care.

**MRI:** Risks will be minimized in the following manner: 1) Subjects will be screened for contraindications as described above. In particular, subjects who have a history of moderate or severe claustrophobia may be excluded at the discretion of the PI. Subjects with a history or possible history of intra-ocular, intracranial, intrathorax, or intra-abdominal metal or cardiac pacemakers will be excluded. 2) Anxiety will be minimized by thoroughly explaining the procedures and the nature of the magnetic resonance scanner to subjects prior to study. During the scanning procedures, the subjects are continually monitored visually and auditorily for any potential problems, and subjects are assured that they can and will be removed from the scanner at any time if problems should arise or they indicate that they are experiencing discomfort. As noted above, subjects will be screened twice prior to study, once at the time of initial contact, and a second time when they arrive at the MRI facility prior to study. All of the data collected for these studies will be kept strictly confidential. Under no circumstances will individually identifiable data be released to anyone without the written consent of the subject. MRI copies of the brain anatomy will be provided to subjects.

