- **Vital signs:** Prior to hormone administration, temperature, heart rate and blood pressure will be measured and recorded by the CRN nurses. Weight and height will be also measured. If heart rate is above 100bpm, or blood pressure is above 140/90, vitals will be re-measured. If levels remain elevated after 3 successive recordings in both limbs (total of 6 recordings) measured at least 5 minutes apart, the study physician will be notified and asked to advise on how to treat the subject and whether it is safe to continue with the protocol. Subjects may still be included at the discretion of the study physician. This is done in order to proceed with baseline vital signs that are within post-hormone administration guidelines. Researcher will ask if the subject is experiencing any adverse events at this time, to provide a baseline before hormone administration.
- **Blood draw:** A registered nurse from the CRN will collect 10 ml of blood by venipuncture for subsequent baseline measurement of plasma oxytocin. Blood will be collected in a lavender-top EDTA-treated tube. Samples will be immediately centrifuged at 4C by the CRN core laboratory and the plasma and blood cells will be stored at -80 until assay at the CRN unit.

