- **Blood draw:** 5 minutes after spray intake, a registered nurse from the CRN will collect 10 ml of blood by venipuncture for subsequent baseline measurement of plasma oxytocin. Blood will be collected in a lavender-top EDTA-treated tube. Samples will be immediately centrifuged at 4C by the CRN core laboratory and the plasma and blood cells will be stored at -80 until assay.
- **Vital signs:** 15 minutes after spray intake, temperature, heart rate and blood pressure will be re-evaluated by the CRN nurse to check for any side effects of IN-OT. There are several pieces of evidence of safety and absence of side effects from chronic and acute intake of IN-OT. Thus, we do not expect any side effects from the hormone oxytocin intake. However, we will ask subjects if they feel any side effects. If no side effects are reported, but temperature has increased or decreased more than 2 degrees, heart rate is above 100 bpm, or blood pressure is above 140/90, the vitals will be re-measured. If levels remain elevated after 3 successive recordings in both limbs (total of 6 recordings) measured at least 5 minutes apart, the study physician will be notified and asked to advise on how to treat the subject and whether it is safe to continue with the protocol. Subjects may still be included at the discretion of the study physician. If subjects were to experience a serious adverse event, such as a heart attack or an anaphylactic reaction, a code will be called and, if necessary, the subject will be taken to the Emory ER. [name] or/and [name] and the CRN nurses will be notified by the experimenter. [name] or [name] will call to admit the subject to the ER. As we already mentioned, it is not likely that oxytocin has any side effects based on the growing evidence in the literature. In addition to vital signs, we will ask participants if they feel any side effects.

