## **Data and Safety Monitoring Plan**

Pre-clinical visit (visit 1) Participants will perform behavioral tests, fill questionnaires, provide saliva DNA samples and conduct training (see above for more details). The training might occur at the Emory hospital or at the Laboratory of Darwinian Neuroscience (as part of the collaboration with [name], PhD) that is located at the anthropology building at Emory University. Participants with ASD might be able to lay down inside the scanner for training purposes to habituate to the context.

We do not expect any serious adverse event and if any adverse event happened during the first visit. We expect several adverse events:

- 1- Tiredness

2- Moderate anxiety or fear reaction in response to lying down in the MRI scanner for ASD.

Participants will be asked how they feel. However, the PI or the experimenter will make sure to take note of these potential adverse events or any unexpected adverse events. All unexpected adverse events related to the first visit will be reported promptly to the IRB and DSMB. All serious adverse events related or not to the first visit will be reported promptly to the IRB, DSMB and to the sponsor. Serious adverse event (based on FDA documentation) includes: life-threatening adverse event, inpatient hospitalization or prolongation of existing hospitalization, a persistent or significant incapacity or substantial disruption of the ability to conduct a normal life functions, or a congenital anomaly/birth defect). Unexpected adverse event is an adverse event that is not listed in the investigator brochure or is not listed at the specificity or severity that has been observed or is not consistent with the risk information described in the protocol.

Severity grading scale for adverse events will be based on this following chart (FDA-based):

- **Grade 1:** mild: asymptomatic or mild symptom; clinical observations only; no intervention indicated
- **Grade 2:** Moderate: minimal, local or noninvasive intervention indicated, have some effect on daily activity
- **Grade 3:** Severe or medically significant that affects daily activity but not immediately life-threatening; hospitalization or prolongation of hospitalization indicated; disabling.

We do not consider any event as related to the study unless if the participant was on-site at Emory with the experimenter. All events that occurred before participants' arrival and after participants' departure will be considered unrelated.

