Clinical visits (4 visits): Each participant will participate in 4 clinical visits at the CRN unit at the Emory Hospital and at BTCI MRI scanner. All the rules below apply for healthy subjects and for patients with ASD.

Based on prior literature, we have a list of expected adverse events that could be linked to oxytocin inhalation or placebo inhalation. This list includes any random symptom that was mentioned in trials previously conducted on single administration of oxytocin and placebo. They are considered random because some of them occurred during placebo spray intake, some of them were not found to be significantly different between placebo and oxytocin, and some of them are mentioned in the medical brochure. The list of expected adverse events includes:

- 1- Nausea or mild nausea
- 2- Vomiting or tendencies to vomit
- 3- Headaches
- 4- Irregularities of the pulse (tachycardia, bradycardia, arrhythmia, very rare hypertension)
- 5- Skin rashes and allergic reactions
- 6- Shortage of breath
- 7- Blood pressure decrease
- 8- Circulatory collapse
- 9- Runny nose

- 10- Tiredness
- 11- Sore throat
- 12- Shakiness
- 13- Sweating
- 14- Coughing

Participants will not be given this list and asked explicitly about it. Instead, the experimenter will ask participants how they are feeling following spray administration.

Participants will be also asked upon arrival on the 2nd, 3rd, 4th and 5th visit if there were any changes in their health.

In this clinical trial, we do not expect serious adverse events, and given that the subject is receiving 3 doses and placebo across 4 different visits (within the same study), we would like to define the terminology of reportable events and a plan to notify the IRB of reportable events:

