**Relatedness:** the PI will consider that any event (serious, unanticipated, death, adverse event, not serious) is related to the treatment only if the event occurred internally during the clinical visit after spray intake (4 clinical visits at CRN unit at Emory Hospital and BITCI MRI scanner at the Emory Hospital). Thus, an event is considered as a related adverse event or a related unanticipated event if it occurred during the few hours of testing (up to 4 hours) and will not be considered related to the treatment once the subject leaves the hospital. The PI will take note of all related expected adverse events (list above) in a log document and report them periodically to the sponsor and the IRB during the continuing review. The PI will report promptly any unanticipated problem (not expected, related, and provides a risk to the participant) to the IRB and to the sponsor. The PI will also report promptly any serious adverse event that is related to the spray intake (that occurred on site visits of CRN unit) to the IRB and the sponsor. The PI will also report to the IRB periodically if any serious adverse event not related to the spray but during the period of the study that occurred off site Emory or before spray intake or after the participant left the hospital and between study visits (please see the definition below of unrelated events). The PI prefers to report promptly any unrelated or related serious adverse events to the IRB and to the sponsor with a precision of relatedness to avoid any problems or misunderstanding. The PI will also report serious adverse events to the sponsor ([name]). The serious adverse events include: death, life threatening experience, hospitalization, disability or permanent damage, medical or surgical intervention, emergency seizures.

Written IND safety reports will be submitted to the FDA by the IND sponsor, for serious, unexpected suspected adverse reactions within 15 calendar days of learning of its occurrence. If the event is fatal or is deemed to be life threatening, the report will be made within 7 calendar days. The IND sponsor will also make an assessment of whether the event constitutes an unanticipated problem posing risks to subjects or others (UP). This assessment will be provided to the Emory University IRB, which, in turn will make a final

determination. If the Emory IRB determines an event is a UP it will notify the appropriate regulatory agencies and institutional officials.

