At least four weeks prior to DSMB meeting, the research coordinator/study staff will prepare a report to be reviewed during that meeting. The report will include the number of participants who signed consent for the study and were randomized, the number of post-randomization dropouts, reasons for these dropouts, and safety concerns, adverse events, etc. An up-to-date consent form will be provided, as well as a summary of measures taken to protect confidentiality (data storage, use of coded ID numbers, etc). The PI will also prepare a report summarizing any new data/evidence that might alter the risk/benefit ratio for participating in the study (such as newly published studies, etc). The PI will report any serious and unexpected adverse events in timely fashion to the Emory DSMB and Emory IRB. Actions taken by the IRB in response to adverse event reports will be immediately reported to the Emory DSMB.

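### The vital-sign rules set no lower limit for pulse or blood pressure, although falls in both are listed as expected events, and no by-dose safety summary is stated

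*Combined protocol and SAP*

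**What the plan says.** Three places set vital-sign rules.

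- **Before the spray** (3- Second visit: clinical visit for ASD). Readings are repeated if heart rate is above 100 bpm or pressure above 140/90. The stated purpose is "in order to proceed with baseline vital signs that are within post-hormone administration guidelines".
- **15 minutes after the spray** (same section). The same upper limits apply, plus a temperature change of more than 2 degrees either way. In both this check and the pre-spray one, the study physician is notified on one condition: "If levels remain elevated after 3 successive recordings in both limbs (total of 6 recordings) measured at least 5 minutes apart".
- **Procedures for minimizing risks, Intranasal OT administration.** With no side effect reported, the trigger is again that "temperature has increased or decreased more than 2 degrees, heart rate is above 100 bpm, or blood pressure is above 140/90". The subject then sits for 10 minutes and is re-measured. The physician or nurse practitioner is contacted if the repeat is not normal.

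On harms, Risks/discomforts and potential benefits says that in rare cases "blood pressure decreases or circulatory collapse are reported as adverse effects of regular and repeated administration of Syntocinon". The Data and Safety Monitoring Plan lists as expected events "Irregularities of the pulse (tachycardia, bradycardia, arrhythmia, very rare hypertension" and, as separate items, a blood pressure decrease and circulatory collapse. Its Grade 1 covers "asymptomatic or mild symptom; clinical observations only". On recording, it says: "The PI will take note of all related expected adverse events (list above) in a log document".

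The Statistical analysis section covers connectivity, BOLD, gaze, social learning, plasma oxytocin and exploratory moderators. It names no summary of vital signs or adverse events by treatment. The DSMB report is to give dropouts, "reasons for these dropouts, and safety concerns, adverse events, etc", with no stated split by treatment.

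**The concern.** The protocol names falls in pulse and pressure as things that may happen after the spray, and calls hypertension very rare. Its numeric pressure rule guards only against the very rare direction. A patient who feels well but has a low reading meets no criterion that requires a second reading or a call to the physician before the scanner. No value is given at which a fall becomes the listed event, so whether it is logged is left to judgement.

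The second, lesser matter is reporting. Each ASD patient is planned to have readings at placebo, 8, 24 and 48 IU, a design well suited to showing what each dose does to pressure and pulse. The risk section expects no significant difference in adverse effects between doses and placebo, but no by-dose breakdown is stated that would show the data on it.

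**Working it through.** **The rule.** There is no plan figure to reproduce, so the check is to apply the post-spray trigger to illustrative readings. Trigger = |temperature change| > 2, or heart rate > 100, or systolic > 140, or diastolic > 90, with no symptoms reported.

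| Reading | Repeat required? |
|---|---|
| 45 bpm, 120/80, no temperature change | No |
| 38 bpm, 80/45, no temperature change | No |
| 70 bpm, 80/45, no temperature change | No |
| 105 bpm, 120/80, no temperature change | Yes |
| 70 bpm, 145/80, no temperature change | Yes |
| 70 bpm, 120/80, temperature down 2.5 | Yes |

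The mention of a normal range under Procedures for minimizing risks does not rescue the low readings. It governs only the re-measurement, which a low pulse or pressure does not prompt. In the visit procedures the physician condition refers to elevated levels only, so it would not, as worded, cover even a persistent fall in temperature, which does prompt a repeat. The pre-spray rule has the same upper limits, so a low starting value is not caught either.

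**Time for a repeat.** The check is at 15 minutes and the resting scan at 40, leaving 40 − 15 = 25 minutes. Three recordings at least 5 minutes apart span at least 2 × 5 = 10 minutes; the other version needs 10 minutes of sitting plus the reading. That leaves at most 25 − 10 = 15 minutes for the escort to the scanner, positioning and the localizer.

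**What a by-dose summary could show.** Randomization and blinding plans 50 ASD patients and allows a stop at 30 or 40.

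- Zero events at a dose, exact one-sided 95% upper limit, 1 − 0.05^(1/n): 9.5% at n = 30, 7.2% at n = 40, 5.8% at n = 50.
- Chance of seeing none if the true rate is 5% (assumed), 0.95^n: 0.215 at n = 30, 0.077 at n = 50.
- Exact paired test with all k discordant patients in one direction, two-sided p = 2 × 0.5^k: k = 5 gives 0.0625, k = 6 gives 0.031.
- Mean dose-minus-placebo difference, 95% half-width = t(0.975, n−1) × SD/√n, unadjusted. The factor is 0.373 at n = 30 and 0.284 at n = 50. For an assumed within-patient SD of 8 to 12 mmHg this gives 3.0 to 4.5 mmHg at n = 30 and 2.3 to 3.4 mmHg at n = 50.

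Mean shifts would thus be estimated usefully under that assumption, whereas event counts would be weak evidence. A zero count or a non-significant test could not support equal safety.

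**The case against.** The strongest reply is that patients are supervised throughout, and much of it stands.

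- Research nurses take the readings to look for side effects, and patients are asked how they feel. Chest pain, difficulty breathing or itching leads to a physician or nurse practitioner call whatever the readings.
- The Blood Draw paragraph has subjects watched for fainting signs, including lowered blood pressure, with monitoring until symptoms settle. One draw comes 5 minutes after the spray.
- In the scanner, subjects are observed by sight and sound and can be removed at any time.

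A reader might infer that a patient with a low reading goes to the scanner unchecked, or that a low reading is never repeated. The documents do not support either. What is missing is a numeric trigger at the 15-minute check: the faint watch belongs to the draw and has no limit.

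A reader might also infer that falls would go unrecorded. They need not: asymptomatic observations can be graded, listed events are logged, and adverse events go to the IRB and DSMB. The annual report also covers adverse events and a treatment review, monitoring analyses of physiological data are possible, and further analysis detail is deferred to amendments. None of these states a dose split, and the physiological measures are listed separately from vital signs under Type of information collected.

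Two further points reduce the weight. The risk section ties these effects to regular, repeated use and calls them rare, and the monitoring plan describes its listed symptoms as random, partly because some occurred on placebo. And Healthy subjects screening indicates that ASD testing is complete, while healthy subjects receive placebo only. A changed limit would therefore help only patients dosed later, for example under the amendment foreseen in Randomization and blinding.

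**Conclusion.** The concern holds as a minor fault in a safety rule. Followed exactly, the stated rules let a symptom-free low pulse or pressure pass with no required repeat or physician call, although the protocol lists such falls as expected events. This is a rule that acts in one direction only, not just missing detail.

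Its clinical size cannot be given: the documents hold no pulse or pressure data, and nothing in them shows that a fall occurred. The table of readings is illustrative. The zero-count limits and paired p-values need no assumption about blood pressure; the 5% rate and the SD of 8 to 12 mmHg are assumptions.

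The missing by-dose breakdown is secondary and, alone, close to a request for an added table. The protocol does not claim equal safety across doses; it states an expectation. The imaging conclusions are unaffected.

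**What to change.** **For any further dosed patients.** In the pre-spray check, the 15-minute check and Procedures for minimizing risks alike:

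1. Make the pulse and pressure limits two-sided, with lower values set by the study physician.
2. After the spray, add a criterion for a fall from that visit's pre-spray reading. The listed event is a decrease, and an absolute limit alone misclassifies. For example, with limits of 50 bpm and 90 mmHg systolic, a man whose usual pulse is 48 would be flagged, while a drop from 135 to 95 would pass.
3. Notify the physician when readings stay outside the limits, not only when they stay high.
4. Log a confirmed fall as the listed event.

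The cost is an occasional repeat of at least 10 minutes, which may be tight before the 40-minute scan.

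**At final analysis, ASD sessions only.** Report dose-minus-placebo differences with 95% intervals for the first post-spray pressure, heart rate and temperature, adjusted for that visit's pre-spray value and visit order, with a patient effect. Tabulate adverse events by the treatment given at that session. Make no equal-safety claim from a non-significant test or a zero count.

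Use the first reading because, under the current rules, repeats of pulse and pressure are prompted by high values and the two repeat schedules differ. Leave out healthy subjects, who receive placebo only and need not be read at 15 minutes. This part costs a paragraph and a few tables from data the protocol already collects, with no new visit.
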